9.6. Pharmacokinetic Analysis

9.6.1. Pharmacokinetic Parameter Calculation Methods

Pharmacokinetic parameters will be calculated by noncompartmental analysis (NCA) method from concentration-time data following these guidelines:

- Actual sampling times relative to end of study drug administration will be used for all calculations of the PK parameters. If there is any doubt as to the actual time a sample was taken, the scheduled time will be used.
- Concentrations from unscheduled PK blood samples will be included in the analysis of the parameters.
- There will be no imputation of missing concentration data.

For the summaries of concentrations and for the NCA analysis of the 0.25% bupivacaine plasma concentrations, concentrations below the limit of quantification (BLOQ) will be handled as follows:

- Pre-dose BLOQ values will be set to zero.
- BLOQ values between the dosing time and the first time point above lower limit of quantification (LLOQ) will be set to 0.
- BLOQ values at time points between two measurable concentration values will be set to ½ of LLOQ (lower limit of quantification).
- All remaining BLOQ values will be set to missing.

The PK parameters will be estimated using the non-compartmental method according to the following guidelines:

- The maximum observed plasma concentration (C_{max}) will be obtained directly from the concentration-time data.
 - \circ Early C_{max} occurring between dosing (0 h) and X hours after dosing if appropriate based on the individual subject and treatment group mean concentration-time plots, where X will be determined from the concentration-time plot.
 - \circ Late C_{max} occurring more than X hours after dosing if appropriate based on the individual subject and treatment group mean concentration-time plots.

where X is a subject-specific local minimum turning point in the concentration-time curve.

- Time to maximum concentration (T_{max}) is the time at which C_{max} is observed.
 - $\circ \quad \mbox{Early T_{max}- the time corresponding to Early C_{max}.}$
 - \circ Late T_{max} the time corresponding to Late C_{max}.
- The apparent terminal elimination rate constant (λ_z) will be estimated at terminal phase by linear regression after log-transformation of the concentrations:
 - Only those data points that are judged to describe the terminal log-linear decline will be used in the regression.
 - \circ A minimum number of three data points in the terminal phase will be used in calculating λ_z with the line of regression starting post the late C_{max} data point (C_{max} will not be part of the regression slope) and including the last point above LLOQ value (Ct).
 - \circ An appropriate number of decimal places will be used for λ_z to enable the reported value of terminal half-life (t_{1/2}) to be calculated.

- Rules for excluding subjects from the terminal phase-related parameter calculation:
 - 1. Adjusted R-square <80%, or
 - 2. %extrapolated AUC >30% of AUC_{0- ∞}
- Apparent terminal half-life $(t_{1/2})$ will be calculated as $\ln(2)/\lambda_z$.
- The area under the plasma concentration-time curve from the time of dosing to the time of the last quantifiable concentration (AUC_{0-last}) will be calculated using the linear-up log down trapezoidal method.
- The area under the plasma concentration-time curve from the time of dosing (zero) to infinity (AUC_{0-∞}) will be calculated as the sum of AUC_{0-last} and residual area C_t/λ_z.
- Extrapolated area under the curve from time of last point above LLOQ (t_{last}) to infinity (AUC_{extr}), expressed as percentage of AUC_{0-∞} will be calculated as (Ct/ λz)/AUC_{0-∞}·100%.
- Apparent clearance CL/F will be estimated as Dose/AUC_{0-∞}, where Dose = 266 mg for subjects receiving EXPAREL, 44 mg (50 mg × 0.886 [salt to free base conversion]) for subjects receiving 50 mg 0.25% bupivacaine, and 87 mg for subjects receive 100 mg 0.25% bupivacaine.
- Apparent volume of distribution (V_d/F) will be estimated as (CL/F) λ_z .

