7.4. Summary of Human Experience with EXPAREL

Pacira has conducted more than 36 clinical studies and one observational follow-up study to investigate EXPAREL. Across these studies, over 1800 human subjects received EXPAREL at doses ranging from 2 mg to 665 mg (equivalent to 2 mg to 750 mg bupivacaine HCl) administered by various routes: local infiltration into the surgical site, subcutaneous, perineural (or nerve block), and epidural. EXPAREL has been generally well tolerated and, in active comparator studies, AEs occurred at a similar rate as the corresponding bupivacaine HCl controls.

EXPAREL was initially approved by the US FDA in 2011 for single-dose administration into the surgical site to produce postsurgical analgesia. The indication was amended and approved by the US FDA in 2018 to read: "EXPAREL is indicated for single-dose infiltration in adults to produce postsurgical local analgesia and as an interscalene brachial plexus block to produce postsurgical regional analgesia." Since its approval, EXPAREL has been administered to approximately 5 million subjects in the US (January 2019).

Following the initial approval of EXPAREL, numerous clinical studies were conducted in which EXPAREL was administered via various routes of administration, including interscalene nerve block (Sternlicht 2014, Feierman 2014).

Please see the [EXPAREL Full Prescribing Information](#) (November 2018) for complete safety information regarding EXPAREL (liposome bupivacaine injectable suspension): <https://www.exparel.com/hcp/prescriptioninformation.pdf>.

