4. STUDY OVERVIEW

This is a Phase 3, multicenter, randomized, double blind, active controlled study in approximately 120 subjects undergoing lower extremity surgeries. This study will have 2 cohorts. Both cohorts will enroll in parallel.

Randomization

Cohort 1 will enroll about 60 subjects undergoing bunionectomy to obtain information on PK profile, PD, efficacy and safety. Subjects in this cohort will be randomized (1:1:1) to receive combined sciatic (in popliteal fossa) and saphenous (in the adductor canal) nerve block with EXPAREL, EXPAREL admixed with 0.25% bupivacaine HCl, or 0.25% bupivacaine HCl.

Cohort 2 will enroll about 60 subjects to obtain information on efficacy and safety. Subjects in this cohort will receive combined sciatic (in popliteal fossa) and saphenous (in the adductor canal) nerve block. Subjects will be randomized (1:1:1) to receive EXPAREL, EXPAREL admixed with 0.25% bupivacaine HCl, or 0.25% bupivacaine HCl, by stratifying by each surgery grouping.

Treatment

For both Cohorts 1 and 2, subjects randomized to the EXPAREL arm will receive 20 mL (266 mg) EXPAREL mixed with 20 mL saline; subjects randomized to EXPAREL admix arm will receive 20 mL (266 mg) EXPAREL admixed with 20 mL (50 mg) 0.25% bupivacaine HCl; subjects randomized to the 0.25% bupivacaine HCl arm will receive 40 mL (100 mg) 0.25% bupivacaine HCl.

Block Procedure

Subjects may be lightly sedated with 1 to 2 mg of midazolam intravenously (IV) before the block procedure. The study drug (EXPAREL, EXPAREL admixed with 0.25% bupivacaine HCl, or 0.25% bupivacaine HCl) will be administered under ultrasound guidance 90 min (\pm 30 min) prior to surgery.

Breakthrough Pain Medication

All opioid and other analgesics administered post-surgery through post-operative day 14 (POD14) will be recorded.

For the initial treatment of breakthrough pain, subjects may receive acetaminophen or NSAIDs.

If the initial pain treatment (acetaminophen or NSAIDs) is insufficient for pain relief, immediate release PO oxycodone may be administered in a stepwise approach:

- Initial dose of 5 mg oxycodone may be offered.
- If the initial opioid dose is insufficient for pain relief, 10 mg oxycodone may be offered.

If a subject is unable to tolerate PO medication or the PO oxycodone pain relief is insufficient, IV morphine (initiated at 2 mg) or hydromorphone (initiated at 0.2 mg) may be administered.

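### SAP 9.6.1 enters 87 mg as the free-base dose for 100 mg bupivacaine HCl, where its own factor gives 88.6 mg, and does not say that the two admix components are summed for CL/F

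*SAP*

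**What the plan says.** SAP 9.6.1 divides a dose by AUC to infinity to obtain CL/F. It gives the first two doses in these words: "where Dose = 266 mg for subjects receiving EXPAREL, 44 mg (50 mg × 0.886 [salt to free base conversion". The sentence goes on "for subjects receiving 50 mg 0.25% bupivacaine, and 87 mg for subjects receive 100 mg 0.25% bupivacaine", with no working shown for the 87 mg. Vd/F is then built on that result: "Apparent volume of distribution (V_d/F) will be estimated as (CL/F", combined with the terminal rate constant.

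The arms are set out in SAP 4. For the admix arm, "subjects randomized to EXPAREL admix arm will receive 20 mL (266 mg) EXPAREL admixed with 20 mL (50 mg) 0.25% bupivacaine HCl". For the comparator, "subjects randomized to the 0.25% bupivacaine HCl arm will receive 40 mL (100 mg) 0.25% bupivacaine HCl". The EXPAREL arm receives 266 mg diluted with saline. No arm receives 50 mg of bupivacaine HCl on its own.

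SAP 9.6.2 works with a single analyte, plasma bupivacaine, and summarizes the PK parameters by treatment. The PK section of the protocol (15.6.3.3) has no dose or conversion rule, and SAP 9.1 gives the SAP precedence over the protocol on statistical methods. SAP 9.6.1 is therefore the only source for these constants.

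**The concern.** Two things do not fit. First, two salt doses in one sentence appear to be converted at different rates: 50 mg with the printed factor, and 100 mg with something smaller. Second, three doses are listed for three arms, but they do not match the arms one to one. Admix subjects meet two of the three descriptions, and the text does not say what to do with the pair.

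CL/F and Vd/F are named PK endpoints (Protocol 12.6, SAP 8.3), and the PK profile of the treatments is part of a secondary objective (Protocol 8.2, SAP 3.2). Dose multiplies CL/F directly, so an error in it shifts every subject in an arm by the same proportion. A reader who sets apparent clearance side by side across arms would then see part of the constant as well as the drug.

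**Working it through.** **Inputs**
- Salt-to-base factor: 0.886 (SAP 9.6.1).
- Doses printed for CL/F: 266, 44 and 87 mg (SAP 9.6.1).
- Doses given: EXPAREL 266 mg; admix 266 mg EXPAREL plus 50 mg bupivacaine HCl; comparator 100 mg bupivacaine HCl (SAP 4).
- EXPAREL strength: 13.3 mg/mL, expressed as base (Protocol 7.3). 20 mL × 13.3 mg/mL = 266 mg, already free base, so it needs no conversion.

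**Step 1. Reproduce the 44 mg.** Base = salt × factor. 50 × 0.886 = 44.3, printed as 44. This agrees.

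**Step 2. Try to reproduce the 87 mg.**
- 100 × 0.886 = 88.6, which rounds to 89.
- Doubling the rounded 44 gives 88.
- Protocol 7.4 gives an outside check on the factor: the upper end of its dose range is "665 mg (equivalent to 2 mg to 750 mg bupivacaine HCl". 665/750 = 0.8867, so 100 mg becomes 88.7 mg.
- Working backwards, 87/100 = 0.870, a factor that appears nowhere in the documents.

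None of these routes gives 87.

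**Step 3. Effect in the bupivacaine HCl arm.** AUC is the same whichever dose is entered, so CL/F scales with the ratio of the doses: 87/88.6 = 0.982, or 1.8% too low. Vd/F is proportional to CL/F and carries the same 1.8%.

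**Step 4. The admix arm.** The measured bupivacaine comes from both products, so the dose that matches the AUC is their sum: 266 + 44.3 = 310.3 mg (310 mg with the rounded 44).

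| Dose entered for admix | Ratio to 310.3 | Error in CL/F and Vd/F |
|---|---|---|
| 266 + 44.3 = 310.3 mg | 1.000 | none |
| 266 mg only | 0.857 | −14.3% |
| 44 mg only | 0.142 | −85.8% |

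**Step 5. What is not affected.** The EXPAREL arm uses 266 mg, which is correct as base. AUC, Cmax, Tmax and half-life do not contain the dose.

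**The case against.** A reader might infer that clearance and volume are wrong in two arms. The documents do not support that. SAP 9.6.1 lists doses by product received, admix subjects receive both products, and nobody receives 50 mg bupivacaine HCl alone. The 44 mg entry therefore has a use only as an addend for the admix arm, and summing is the one reading that gives every entry a sensible purpose. It leads to about 310 mg, which is right. The 14.3% and 85.8% figures need an analyst to drop one component, and nothing in either document tells them to. This objection stands. What remains is that the sum is left to inference in a plan meant to fix such things in advance.

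It can also be said that the mistake may lie in the factor and not in the 87 mg. The 44 mg does not decide between them: 50 × 0.870 = 43.5 also rounds to 44. The protocol's 665/750 ratio favours 0.886, although it comes from a rounded range whose lower end equates 2 mg with 2 mg. This stands in part: the two printed numbers conflict, and the evidence in the documents points to 0.886, but the sponsor has to confirm it.

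Finally, 1.8% is small. PK is summarized descriptively, with no planned test between arms, and the same section keeps subjects with up to 30% of AUC extrapolated. A constant multiplier can also be corrected later without new data. All of that is true and limits the importance of the point. It does not make the constant consistent with the factor printed in the same sentence.

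**Conclusion.** The point holds in two limited parts. The 87 mg is inconsistent with the SAP's own 0.886 factor and, if used, makes CL/F and Vd/F in the bupivacaine HCl arm about 1.8% too low. This assumes that 0.886 is the intended factor, as both the SAP and the protocol's ratio indicate. In the admix arm the analysis dose is ambiguous: the results are right if the components are added, and the larger errors would arise only from a misreading.

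Both parts concern descriptive Cohort 1 parameters. The primary endpoint, its power and the type I error are untouched. It is a small correction, worth making because it is demonstrable and nearly free.

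**What to change.** In SAP 9.6.1, reconcile the 87 mg with the 0.886 factor: either enter 88.6 mg, which is what that factor gives, or state and justify a different factor and apply it to both salt doses. Then replace the list by product with the free-base analysis dose by arm. With the 0.886 factor these are EXPAREL 266 mg, EXPAREL admix 266 + 44.3 = 310.3 mg (stated as the sum of its two components), and bupivacaine HCl 88.6 mg.

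The cost is one SAP sentence and the matching constants in the PK program. Nothing changes in the data, the design or any dose administered to subjects.

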9.6.2. Pharmacokinetic Concentrations and Variables

The analysis of the PK parameter will be based on the PK analysis set. The analysis of the PK concentration will be based on the Safety analysis set.

Bupivacaine plasma concentrations will be listed by treatment, subject, nominal time, and actual time. Concentrations that are BLOQ will be indicated in this listing.

Plasma concentrations will be summarized at each nominal time point seperately for each treatment. The following descriptive statistics will be presented: n, arithmetic mean, SD, geometric mean, %CV, median, minimum and maximum.

Pharmacokinetic parameters will be summarized by treatment. Descriptive statistics for PK parameters except for T_{max} will include: n, arithmetic mean, SD, geometric mean, %CV, median, minimum and maximum values. Descriptive statistics for T_{max} (early and late) values will include n, median, minimum and maximum values.

Individual plasma concentration versus actual times will be plotted for each subject in linear and semi-logarithmic scales, placed on the same page. Mean plasma concentration at the scheduled time points will be plotted for each treatment in linear and semi-logarithmic scale, with the associated standard errors (for linear scale only) at each scheduled time point.

In the plot for individual subjects, concentrations that are below the limit of quantitation (BLOQ) will be assigned a value of $\frac{1}{2}$ LLOQ if they are collected postdose.

If there are detectable (non-BLOQ) concentration values at pre-dose that are >5% of global C_{max} for the respective subjects, these concentration values and PK parameters from subjects with these values will be excluded from descriptive statistic summaries.

9.7. Pharmacodynamic Analysis

9.7.1. Sensory Function

Separately for sciatic and saphenous nerve, time to onset of sensory block from end of study drug administration and duration of sensory block will be summarized by the median and quartiles estimated using the Kaplan-Meier method similar to Section 9.5.2.2. See Section 9.5.2.4 for how to handle censoring time.

The number (and %) of subjects with normal sensation and no sensation will be tabulated by treatment group and timepoint. Because patients are not required to continue the onset or offset assessment after they have reached the onset or offset respectively, missing scheduled assessment will be imputed using the last observation carried forward (LOCF) method.

Additionally, mean PK concentration and % subjects with motor block "on" will be overlaid and plotted over time to show the dynamic relationship between the two for each of the 3 treatment groups.

9.7.2. Motor Function

Time to onset of motor block from end of study drug administration and duration of motor block will be summarized by the median and quartiles estimated using the Kaplan-Meier method similar to Section 9.5.2.2. Cumulative subject incidence plot (1 - [minus] Kaplan-Meier curves) will also be presented.

The number (and %) of subjects with complete motor function and partial/no motor function will be tabulated by treatment group and timepoint. Missing assessment will be imputed by LOCF.

Additionally, PD plot similar to the one described in Section 9.7.1 will be created for the sciatic distal and saphenous distal sensory nerves.

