7.3. EXPAREL (Bupivacaine Liposome Injectable Suspension)

Bupivacaine is one of the longer-acting local anesthetics, but even so it has a limited duration of action after local administration, usually less than 8 hours. EXPAREL (Pacira Pharmaceuticals, Inc., ["Pacira"]) is a bupivacaine liposome injectable suspension. It consists of microscopic spherical, multivesicular liposomes (DepoFoam® drug delivery system) organized in a honeycomb-like structure comprising numerous non-concentric internal aqueous chambers containing a bupivacaine base at a concentration of 13.3 mg/mL. Each chamber is separated from adjacent chambers by lipid membranes. The lipids (phospholipids, cholesterol, and triglycerides) are naturally occurring or close analogs of endogenous lipids. Bupivacaine is slowly released from the DepoFoam particles by a complex mechanism involving reorganization of the barrier lipid membranes and subsequent diffusion of the drug over an extended period of time.

EXPAREL was approved by the US FDA in 2011 for administration into the surgical site to produce postsurgical analgesia. The active ingredient (bupivacaine) and inactive ingredient (DepoFoam) of EXPAREL are each contained, though separately, in FDA-approved products.

- Bupivacaine hydrochloride (HCl) solution, a well-characterized anesthetic/analgesic, with more than 35 years of use in the US.
- DepoFoam, a liposomal extended-release formulation contained in the marketed product DepoCyt® (1999). The form of DepoFoam used in EXPAREL has a slightly different mixture of liquid components than that used in DepoCyt.

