The beginning of surgery is defined as the time of the first incision.

End of Surgery

The end of surgery is defined as the time recorded in the surgical record.

Postsurgical

Postsurgical is defined as after the end of surgery.

Time Window for Numeric Rating Scale (NRS) for Scheduled Pain Score Collection

Table below provides the time window for the NRS pain score for analysis. If multiple scheduled or unscheduled assessments occur within the same window, the assessment closest to the scheduled time will be chosen. If the assessments are equidistance the later will be chosen.

Scheduled Time of Collection	Time Window for Acceptable Actual Time of Collection
6-hour	From PACU arrival to 9-hour
12-hour	From >9-hour to 15-hour
18-hour	From >15-hour to 21-hour
24-hour	From >21-hour to 27-hour
30-hour	From >27-hour to 33-hour
36-hour	From >33-hour to 39-hour
42-hour	From >39-hour to 45-hour
48-hour	From >45-hour to 51-hour
54-hour	From >51-hour to 57-hour
60-hour	From >57-hour to 63-hour
66-hour	From >63-hour to 69-hour
72-hour	From >69-hour to 75-hour
78-hour	From >75-hour to 81-hour
84-hour	From >81-hour to 87-hour
90-hour	From >87-hour to 93-hour
96-hour	From >93-hour to 99-hour

 Table 3. Time Window for the NRS Pain Score Collected at Scheduled Time Points Post-Surgery

Time Window for Sensory and Motor Block Tests

Table below provides the time window for the sensory block and motor block summaries by timepoint (Sections 9.7.1 and 9.7.1).

Scheduled Time of Collection	Time Window for Acceptable Actual Time of Collection
Predose	Predose
15-min	From end of study drug administration to 22.5-min
30-min	From >22.5-min to 37.5-min
45-min	From >37.5-min to 52.5-min
1-hour	From >52.5-min to 1.5-hour
2-hour	From >1.5-hour to 5-hour
8-hour	From >5-hour to 10-hour
12-hour	From >10-hour to 18-hour
24-hour	From >18-hour to 27-hour
30-hour	From >27-hour to 39-hour
48-hour	From >39-hour to 54-hour
60-hour	From >54-hour to 66-hour
72-hour	From >66-hour to 78-hour
84-hour	From >78-hour to 90-hour
96-hour	From >90-hour to 108-hour
120-hour	From >108-hour to 132-hour
144-hour	From >132-hour to 156-hour
168-hour	From 156-hour to 180-hour

Table 4. Time Window for the Sensory and Motor Block Tests at Scheduled Time Points Post-Study Drug Administration

Oral Morphine Equivalent Dose (OMED)

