Onset of motor block will be defined as the earliest timepoint with 2-point score of 1- Partial or no foot movement as opposed to 0- Complete foot movement. If subject does not experience loss of motor, their onset will be censored at their last available motor assessment time point prior to surgery. **Offset of motor block** will be defined as resolution of motor block at foot, first time point of the two consecutive recovery assessments (score 0- complete foot movement) (excluding Not Done assessment). If offset time is not achieved, it will be considered censored at the last offset assessment time after surgery. After offset of motor block is noted (on 2 consecutive assessments), no subsequent assessments will be required. If the patient's motor block is recovered at the last assessment to confirm, the motor block is considered recovered at this last time point. **Duration of motor block** will be defined as time between onset and offset of motor block. The censoring and missing data rule for the duration of sensory block also applies to the duration of motor block.

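### LOCF for every missing sensory or motor assessment tabulates a Cohort 1 subject lost before offset as blocked through 168 h, while the duration analysis censors that subject

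*SAP*

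**What the plan says.** For Cohort 1, SAP 9.7.1 and 9.7.2 plan tables of block status by arm and scheduled time. For motor function: "The number (and %) of subjects with complete motor function and partial/no motor function will be tabulated by treatment group and timepoint". A parallel table covers sensation. SAP Table 4 takes these summaries to the 168 h visit, whose window is "From 156-hour to 180-hour".

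On missing assessments, SAP 9.7.1 first gives a reason, "Because patients are not required to continue the onset or offset assessment after they have reached the onset or offset respectively", and then the rule: "missing scheduled assessment will be imputed using the last observation carried forward (LOCF) method". SAP 9.7.2 has the rule without the reason: "Missing assessment will be imputed by LOCF".

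The duration variables are handled differently. SAP 6.3 says: "If offset time is not achieved, it will be considered censored at the last offset assessment time after surgery". SAP 9.5.2.4 then enters all censored durations as right censored in the Kaplan-Meier and log-rank analysis.

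SAP 9.7.1 also plans a PK/PD display: "mean PK concentration and % subjects with motor block 'on' will be overlaid and plotted over time". SAP 9.7.2 plans a similar plot for two sensory sites. Neither section says whether the plotted percentages come from the LOCF-imputed data.

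**The concern.** The reason given covers one kind of gap, the planned end of testing. After offset, carrying recovery forward is sound. The rule reaches every gap, including withdrawal and missed visits before offset. There the last state is blocked, and LOCF holds it to 168 h with no observation behind it.

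The onset half of the reason does not help. Under protocol Table 2 (note b) and Section 12.7, testing ends only after offset on two consecutive evaluations, so reaching onset creates no planned gap. Taken literally, it would license carrying block forward.

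At stake is the tail of the percent-blocked display. Losses while blocked put an artificial plateau on it, in whichever arm has more of them. A state of blocked at 168 h is not neutral: protocol 13.10 provides for unscheduled visits when a deficit persists then, and persistent numbness and weakness are events of special interest. If the overlay uses the imputed data, its two curves would also describe different subjects, because SAP 9.6.1 rules out imputing concentrations.

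**Working it through.** The plan states no figure that depends on this rule, so there is nothing to reproduce. I compared the texts, then counted.

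**Inputs.** 20 subjects per arm in Cohort 1 (protocol 11.1). Percentages by default use the arm within the analysis set as denominator (SAP 9.1). Scheduled times come from protocol Table 2. Six subjects are excluded from the sensory evaluation (SAP 6.4). No dropout rate is given, so the number lost while blocked, k, is assumed to be 1 to 3 per arm.

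**Step 1: rules side by side.**

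| Kind of gap | Within the stated reason? | By-timepoint table | Duration analysis |
|---|---|---|---|
| After offset, testing stopped as planned | Yes | Recovered carried forward | Event at offset |
| Between two observed assessments, such as during surgery | No | Last state held until next observation | Follow-up continues |
| Lost before offset | No | Blocked carried to 168 h | Censored at last assessment |

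The problem is in the last row. The early-termination list in protocol 10.3.3 has pain scores, an e-diary reminder and a safety call, but no sensory or motor test, so a withdrawing subject's blocked record need not be updated.

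**Step 2: size per subject, motor table.** Suppose k subjects are lost while blocked and all others recover by 168 h. LOCF shows k/20 blocked at 168 h: 1/20 = 5%, 2/20 = 10%, 3/20 = 15%. With those values left missing, the table shows 0/19, 0/18 and 0/17. The 5 points are an upper figure: they measure the difference from that subject having in fact recovered.

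For sensation the denominator may be below 20. The split of the six exclusions by arm and cohort is not given. If all six were in one Cohort 1 arm, one subject would be 1/14 = 7.1 points; if two were in each arm, 1/18 = 5.6 points.

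**Step 3: shape of the curve.** Assumed: 20 subjects, 2 lost after 24 h while blocked; 4, 5, 4, 3 and 2 recover at 30, 48, 60, 72 and 96 h.

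| Time | LOCF as written | Lost subjects left missing | Kaplan-Meier |
|---|---|---|---|
| 30 h | 16/20 = 80.0% | 14/18 = 77.8% | 77.8% |
| 48 h | 11/20 = 55.0% | 9/18 = 50.0% | 50.0% |
| 60 h | 7/20 = 35.0% | 5/18 = 27.8% | 27.8% |
| 72 h | 4/20 = 20.0% | 2/18 = 11.1% | 11.1% |
| 96 to 168 h | 2/20 = 10.0% | 0/18 = 0% | 0% |

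**Step 4: check of the obvious remedy.** The last two columns agree only because both losses precede every recovery. Suppose instead that 10 of 20 recover by 24 h, 2 of the 10 still blocked are then lost, nobody recovers by 30 h, and 4 of the remaining 8 recover by 48 h.

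| Time | LOCF as written | Assessed or already recovered as denominator | Kaplan-Meier |
|---|---|---|---|
| 30 h | 10/20 = 50.0% | 8/18 = 44.4% | 10/20 = 50.0% |
| 48 h | (4+2)/20 = 30.0% | 4/18 = 22.2% | 0.50 × (1 − 4/8) = 25.0% |

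A denominator that keeps recovered subjects and drops blocked losses is too low, and at 30 h it is worse than LOCF.

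**The case against.** The strongest reply is about reach. The rule governs descriptive tables only. The tested motor-block duration and the onset and duration summaries use Kaplan-Meier methods with censoring. A reader might infer that LOCF biases the secondary endpoint; the SAP does not support that, since 6.3 and 9.5.2.4 never use the imputed table. A reader might also infer that the overlays are certainly distorted. The LOCF sentences sit with the tabulations, and the source of the plotted percentages is not stated, so that part is conditional. Both limits stand.

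Loss while blocked should also be uncommon, because Cohort 1 is discharged only after the 168 h assessments (protocol 13.8). A subject with very little data might fall outside the pharmacodynamic set (protocol 15.4), although the plan allows censored durations, so exclusion is not assured. The SAP text between Sections 6.4 and 8 was not available to me and may say more on this.

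A striking example is a bupivacaine HCl subject last seen blocked at 2 h and then shown blocked at all 12 later times, against the protocol's remark that "it has a limited duration of action after local administration, usually less than 8 hours". The count is right, but the remark concerns local administration in general, not motor recovery after this block, and the subject would have to miss 12 consecutive assessments. It is not evidence of likely size.

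Two textual replies remain. First, the reason in 9.7.1 could be read as limiting the rule, with 9.7.2 a shortened repeat. The operative words set no such limit, and 9.7.2 does not refer back to the reason. Second, a fixed-denominator table and a censored estimate are different summaries, so different handling is not in itself a contradiction. That is fair. The fault is that the table presents an unobserved state as observed.

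**Conclusion.** The point holds in a limited form. As written, the two LOCF sentences tabulate a Cohort 1 subject lost before offset as blocked through 168 h, for a reason that does not apply to that subject, while the duration analysis censors the same subject. This is a stated rule that gives a wrong display, not a missing detail.

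The size is up to 5 percentage points per such subject at later times in the motor table with 20 per arm, and possibly somewhat more for sensation. With an assumed one to three losses per arm, that is 5 to 15 points at 168 h. The actual number may be zero. The finding covers the descriptive by-timepoint tables for certain, and the overlay plots only if they use the same data. The primary endpoint, the tested duration of motor block and the Kaplan-Meier summaries are unaffected. This is a low-priority correction, worth making because it is cheap.

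**What to change.** In SAP 9.7.1 and 9.7.2:

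- Limit LOCF to (a) time points after offset as SAP 6.3 defines it, including the provision that recovery seen at the last assessment counts as recovery, and (b) gaps between two observed assessments, such as during surgery. Requiring two confirmations for (a) would create a new mismatch with 6.3.
- Do not carry block past the last assessment of a subject without offset. Show the number assessed at each time point.
- Take the percent-blocked curve after onset from a Kaplan-Meier estimate of time from end of study drug administration to offset, with the censoring already in SAP 6.3. Do not use a denominator that keeps recovered subjects and drops blocked losses. State that the estimate assumes subjects lost while blocked would have recovered like those still followed.
- State which data feed the PK/PD overlays.

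The cost is a few sentences and one extra derivation. The planned duration runs from onset, whereas PK time runs from end of administration, so the existing Kaplan-Meier curve cannot be reused directly. Late denominators in the tables become slightly smaller.
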